8.5 Are you performing a social or behavioral study?	
⊙ Yes C No	
8.6 Are you performing a biomedical study?	
O Yes ⊙ No	
8.7 Are you performing a clinical trial?	
O Yes ⊙ No	
8.8 Are you conducting a chart review only?	
O Yes ⊙ No	

### 9.0 Study Details

- 9.1 Provide a step-by-step description of the research procedures, study schedule, and interactions with human subjects:
  - Submit all data collection tools that will be used in the study in the Initial Review Submission Packet.

There are three separate study populations for this study, with procedures and instruments specific to each population.

- 1) The first population is seriously ill patients served by the participating dialysis centers and CKD practices. (Instruments A, E, and F)
- 2) The second population is staff of the dialysis center and associated nephrology practices and associated palliative care programs. (Instrument B)
- 3) The third population is a subset of clinical staff who are actively participating with the change team. (Instrument C)

#### A. Patient-reported outcomes (telephone survey)

Summative evaluation - before and after the learning collaborative.

To measure whether the intervention of the learning collaborative has impacted patient reported outcomes, we will interview seriously ill patients at the participating dialysis centers. We have developed a questionnaire based on several standardized measures relating to shared decision making, advance care planning, and end of life discussions. The survey will be administered by telephone and takes about 20 minutes. We will survey patients selected from the dialysis center patient population in a baseline period prior to the start of learning collaborative activities. We will then survey another cohort of patients at the completion of the 18 months of collaborative activities.

# B. Staff perception of organizational competence in delivering supportive kidney care - Kidney Supportive Care Implementation Quotient (KSC-IQ on-line survey)

Summative evaluation - before and after the learning collaborative.

We have designed an on-line survey that assesses staff perception of how well their organization delivers supportive kidney care. Survey questions are tied to the best practices in the evidence-based change package. The survey link will be distributed to all local staff associated with the dialysis center, associated nephrology offices, and palliative care or hospice organizations cooperating with the dialysis center. The survey will be conducted at baseline prior to inception of the collaborative. Survey results will be shared with the participating organizations to use as a needs assessment. The survey will be conducted again after the close of the collaborative.

C. Clinical staff and change team perception of integration of new practices - NOMAD survey (online) Both formative and summative evaluation.

We will administer the NOMAD survey to measure staff perception (all dialysis center clinical staff) about the extent to which Pathways best practices have become part of normal work flow. Based on Normalization Process Theory. All dialysis center clinical staff will be invited to complete the survey after the first and third learning periods. Change team participants will be especially encouraged to complete the survey as part of their participation on the change team.

#### D.Facility monthly report of utilization statistics

Formative evaluation - monthly reports during 18 months of the collaborative.

To assess interim progress of sites in implementing changes, each change team will submit a monthly report providing aggregate monthly information on utilization indicators such as the number of patients assessed as seriously ill, number of patients with completed advance directive, number of patients using hospice. (See attached in study documents).

#### E. Baseline and follow-up patient demographic and utilization data

During the 4 month baseline and 4 month follow-up periods, we will collect de-identified patient-level data for patients identified as seriously ill. The data to be collected is similar to the utilization statistics collected in (D) above, supplemented with demographic and health status data to allow a comparison between patients who participate in the patient survey (A above) and those who are ineligible to participate. This data will allow us to assess generalizability of the patient survey results. These data will also be linked to the patient survey in order to link patient reported outcomes with health utilization outcomes.

#### F. Pathways MMWD CKD Intervention Tracker

For CKD sites only. The tools we created for use in dialysis centers (D, E) are not practical for CKD clinics. The clinics are unable to identify a patient group to serve as the background (denominator) population for the Seriously Ill/Medical Management Without Dialysis (SI/MMWD) patients, so in this simplified version, we track only de-identified patient data for the SI/MMWD patients, not overall clinic numbers. We have come to regard the CKD clinic piece as a pilot side project and may adapt the collection instrument - without collecting any unapproved data - in collaboration with clinics as we figure out what is feasible.

Procedures for each of these studies is further described:

#### A. Patient-reported outcomes (telephone survey)

The steps in the procedure for the subjects who are patients are as follows:

- 1. The subjects (ESRD patients), who are being treated at participating dialysis centers and CKD practices and are identified as "seriously ill" by clinic staff using the screening tool, will form the population from which patients will be selected. We plan to survey 360 patients across the 15 participating sites during the baseline period. We will select a separate cohort of another 360 patients to interview at the completion of the 18-month learning collaborative.
- 2. Identified subjects will be approached by a member of the dialysis organization or CKD practice. The nature of the study will be explained. If the patient agrees to be contacted to learn more about the study, their contact information will be shared with the WVU CTSI and a research coordinator from WVU CTSI will contact the patient to explain the study. If the patient is interested, the interviewer will provide information needed for informed consent and will obtain verbal consent to proceed. A copy of the information provided during verbal consent process will be mailed to patients who consent along with the incentive gift card.
- 3. The subjects who give verbal consent will be interviewed as described in the attached patient questionnaire.
- 4. A "thank you" incentive of a \$25 gift card will be mailed to patients who complete the survey.

# B. Staff perception of organizational competence in delivering supportive kidney care - Kidney Supportive Care Implementation Quotient (KSC-IQ on-line survey)

The steps in the procedure for the subjects who are dialysis center personnel or personnel with associated nephrology practices are as follows:

- 1. The dialysis center or nephrology practice will have the option of an on-line survey or a paper survey to distribute to staff. We have added the paper survey option because many of the dialysis center and nephrology practice staff have no or very limited access to internet at the worksite. For the on-line survey option, we will ask the dialysis center and/or nephrology practice to send a survey link to all of its staff. Some change teams may also be working closely with associated nephrology practices and/or palliative care teams or hospice teams. In the case where the change team has identified such partner organizations, those organizations will send a survey link to all of its staff.
- 2. The survey will start with a page which explains the purpose of the survey and describes risks and benefits of participating in the survey. The survey contains a question asking for electronic consent, as follows:

ELECTRONIC CONSENT: Please select your choice below. Clicking on the "Agree" button below indicates

- \* You have read the above information
- You voluntarily agree to participate

\* You are at least 18 years of age

Agree

Disagree (this will end the survey)

3. Survey results will be anonymous. However, surveys will be traceable to a particular dialysis center.

#### C. Clinical staff and change team perception of integration of new practices - NOMAD survey (online)

- 1. The dialysis center will have the option of an on-line survey or a paper survey to distribute to staff. We have added the paper survey option because many of the dialysis center staff have no or very limited access to internet at the worksite.
- 2. For the online survey, the dialysis center or nephrology center will send an on-line survey link to all of its clinical staff.
- 3. The on-line survey will start with a page which explains the purpose of the survey and describes risks and benefits of participating in the survey. The survey contains a question asking for electronic consent, as follows:

ELECTRONIC CONSENT: Please select your choice below. Clicking on the "Agree" button below indicates that:

- \* You have read the above information
- \* You voluntarily agree to participate
- \* You are at least 18 years of age

Agree

Disagree (this will end the survey)

- 4. The paper survey will have the same informed consent text as the on-line survey. Presumably, staff who do not consent to participate will not submit the paper survey.
- 5. Members of the change team in particular will be strongly encouraged by the Pathways Project staff to complete the NOMAD survey at designated times through email reminders and reminders on regularly scheduled calls.

Change team selection and consent

- The subjects who are part of the intervention team in each dialysis center or associated CKD practice will be identified by the dialysis or CKD clinic management.
- 2. The identified team members will be approached by the research coordinator who will describe the surveys to be completed as part of the study and the time when each survey will need to be completed. The surveys and their timing are listed on the attached measures spreadsheet. Copies of the surveys are also attached. The surveys are the Kidney Supportive Care Implementation Quotient, the NoMAD implementation tool, and the Institute for Healthcare Improvement single-item measure of the dialysis personnel's sense of the progress of the intervention in his/her dialysis center.
- The dialysis or CKD clinic research coordinator will ask for verbal consent from the subject to participate.
- 4. The subjects who give verbal consent will be asked to complete the surveys at the intervals specified in the measures spreadsheet. The Kidney Supportive Nephrology Care Implementation Quotient and the NoMAD implementation tool only need to be completed twice. The Institute for Healthcare Improvement single-item measure needs to be completed monthly (but only by the head of the change team).

### D. Facility-level monthly report of utilization statistics

The monthly report to be filed by each dialysis center or associated CKD practice provides aggregated data at the clinic level. To collect this data, a designated staff person will fill out a worksheet that collects the necessary information about all seriously ill patients served by the dialysis center or associated CDK clinic in that month. This worksheet will have a separate line for each seriously ill patient where the utilization statistic (such as whether hospitalized in the month, duration of hospitalization), can be entered. Alternatively, the staff person will query their database for the data on the utilization statistics (such as number of hospitalizations). The worksheet will then tally across the entire patient population for that month. The staff person will transfer the AGGREGATED TOTAL to the monthly reporting form, for submission via secure upload via REDCap. Alternatively, for sites that do not establish connection with REDCap, they securely email the form to a member of the Pathways research staff. The worksheet with

information for individual patients will NOT be transmitted to GW. The sites will be instructed to store those individual worksheets for the duration of the project, should there be a need to audit the aggregated monthly statistics. In addition to the monthly report of utilization statistics, the dialysis center or associated CKD practice staff will provide short progress report on their activities in implementing the Pathways change package. E. Patient-level demographic and utilization information During 4 month baseline and 4 month follow-up period, the site will provide de-identified person level data ONLY for seriously ill patients. The reason for doing this is to allow comparison between seriously ill patients who consent to the survey vs. those who are not eligible or do not provide consent for the survey to determine the generalizability of the survey results. Optionally, sites may choose to provide deidentified patient-level data during the interim months. This instrument also includes a chart audit of advance care planning conducted once during the baseline period and once during the followup period. See attachment:(i nclude patient level template and chart audit template). Each subject will be identified by a study identifier assigned by the site. A code link between the study identifier and the patients name and/or dialysis/CKD center identifier will be maintained by the site in a locked file. The purpose of the site code link is to allow the site to pull the correct information from clinic records to record in the data collection form. A different code link for patients who agree to participate in the survey will be kept in REDCap, and will only be accessible by the WVU study coordinator. The purpose of this codelink is to determine which of the patients on the data submitted by the sites corresponds to which patient survey. F. Pathways MMWD CKD Intervention Tracker The CKD site will provide de-identified person level data ONLY for the Seriously Ill/Medical Management Without Dialysis (SI/MMWD) patients, not overall clinic numbers. The data we collect will be suitable only for descriptive analysis, but will provide information and experience towards future, more systematic efforts Each subject will be identified by a study identifier assigned by the site. A code link between the study identifier and the patients name and/or dialysis/CKD center identifier will be maintained by the site in a locked file. The purpose of the site code link is to allow the site to pull the correct information from clinic records to record in the data collection form. 9.2 Will subjects be audio-recorded, video-recorded, or photographed? Check any that apply. Audio-recorded ☐ Video-recorded Photographed 9.6 Describe alternatives to the study procedures (ex: not to participate, standard care): A. Patient-reported outcomes (telephone survey) If the patients choose not to participate in the telephone surveys they will receive standard care. B. Staff perception of organizational competence in delivering supportive kidney care - Kidney Supportive Care Implementation Quotient (KSC-IQ on-line survey) Staff participation in the survey is voluntary and no one will know who participated or not. If participation rates are low overall, management may exhort general increase in participation through posters, emails, discussions at staff meetings - but these will be general and not directed to an individual staff person. C. Staff change team perception of integration of new practices - NOMAD survey (online) Same as above for KSC IQ survey D. Facility-level monthly report of utilization statistics and average patient Collaborate score. Filing monthly reports is a requirement of participating in the collaborative. If a change team director repeatedly fails to provide monthly reports, the site may be asked to leave the collaborative. E. Patient level demographic and utilization information Patients who decline to release their utilization information will receive standard care. F. Pathways MMWD CKD Intervention Tracker Patients who decline to release their utilization information will receive standard care. 10.0 Subject Population

# 10.1 General description of the study population: A. Patient-reported outcomes (telephone survey)

The study population of subjects will include 720 dialysis patients who were determined to be seriously ill according to the "surprise question" screening tool. (360 at baseline and 360 at the end of the study 18 months later. This includes about 20 patients for pre-testing the survey.)

# B. Staff perception of organizational competence in delivering supportive kidney care - Kidney Supportive Care Implementation Quotient (KSC-IQ on-line survey)

All current employees of the participating dialysis center or associated CKD practices will be invited. The number of staff is not currently known, but it likely ranges from about 40-50 personnel per site. In some cases staff of associated offices will also be invited (for instance, staff of the clinics or offices operated by nephrologists associated with the site). This invite will be extended if the change team is implementing change practices in conjunction with the nephrology clinic or palliative care clinic. Total respondents anticipated: up to 750 staff members at baseline. 750 repeated at follow-up. Many of these may be the same staff person, but we will not be tracking that, so will count staff members each time they answer the survey.

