   and Nephrology practices and dialysis centers engaging in collaborative efforts with palliative care
   and hospice programs for seriously ill patients with CKD and ESRD.

The potential longer-term impact could result in:

- More patients reporting end-of-life care discussions with their nephrologist and other clinicians;
- More patients with advanced CKD choosing medical management without dialysis (literature from other countries suggests there could be a five-fold increase);
- More patients choosing palliative dialysis;
- More patients referred to palliative care and hospice; and
- Patients reporting a higher quality of life because of better pain and symptom assessment and management.

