#### 10.6 Inclusion Criteria:

Order Number	Criteria
1	Patients at least 18 years old who are currently being treated by participating dialysis center.
2	Dialysis patients identified as "seriously ill" by screening with "surprise question"- a validated tool that identifies patients with elevated mortality risk. The treating nephrologist or nurse practitioner or dialysis nurse answers whether they would be surprised if the patient died in the next 6 months.
3	For staff surveys only: Dialysis personnel working in the participating dialysis centers or associated nephrology practice or associated palliative care practice.

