#### 13.2 Describe the informed consent process, assent process, and parental permission process:

A. Patient-	B. Kidney	C. Clinical	D. Facility	E. Baseline
reported	Supportive	staff and	level monthly	and follow-
outcomes	Care	change team	report of	up patient
(telephone	Implementation	perception of	utilization	demographic
survey)	Quotient (KSC-	integration of	statistics	and
	IQ) on-line	new practices		utilization
	survey with	- NOMAD		data
	paper option	survey		(including
				chart audit
				for advance
	reported outcomes (telephone	reported outcomes (telephone survey)  Supportive Care Implementation Quotient (KSC-IQ) on-line survey with	reported outcomes (telephone survey)  Supportive change team perception of integration of new practices survey with  Supportive staff and change team perception of integration of new practices - NOMAD	reported outcomes (telephone survey)  Supportive change team perception of Quotient (KSC-IQ) on-line survey with  Supportive staff and change team perception of integration of new practices survey with  Supportive change team perception of integration of new practices survey with

			on-line survey with paper option		care planning)
Population	"Seriously ill" patients at dialysis center	All staff of dialysis center, and associated nephrology practices and /or palliative care practices	Clinical staff of dialysis center or CKD practice	Patients served by dialysis center or ESRD Stage 4 & 5 patients of CKD practice	"Seriously ill" patients at dialysis center or CKD practice
Level of data collection	Individual	Individual	Individual	Aggregate (by center)	Individual
Consent	Waiver of documentation (already IRB approved)	Electronic consent for on- line. Check box consent (no name) for paper survey.	Electronic consent for on-line. Check box consent (no name) for paper survey.	N/A	Waiver of Consent
Consent type	verbal	Electronic or paper	Electronic or paper	N/A	N/A
Consent process	WVU interviewer reads consent script and asks for consent. (script already IRB approved). Copy of study information mailed to survey participants along with \$25 incentive gift.	Self administered - Study information provided included in written form at beginning of questionnaire.	Self administered - Study information provided included in written form at beginning of questionnaire	N/A	N/A

Instrument: MMWD CKD Intervention Tracker

Population: "Seriously ill"/Medical Management without Dialysis patients at CKD practice

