16.6 Is there a data and safety monitoring plan or board (DSMB) for this study?  O Yes • No	
C Yes    No	
O Yes ⊙ No  Privacy and Confidentiality	
O Yes    No  Privacy and Confidentiality  17.1 Which personal or demographic data will be collected?	
O Yes	
Privacy and Confidentiality  17.1 Which personal or demographic data will be collected?  Check all that apply:  Name SSN Medical Record # (MRN) DOB Age Phone # Home Address Email	
Privacy and Confidentiality  17.1 Which personal or demographic data will be collected?  Check all that apply:  Name SSN Medical Record # (MRN) DOB Age Phone # Home Address Email Date of medical procedures	
Privacy and Confidentiality  17.1 Which personal or demographic data will be collected?  Check all that apply:  Name SSN Medical Record # (MRN) DOB Age Phone # Home Address Email	

☐ Department / ☐ Disease Status ☐ City ☐ State / other ☐ Zip Code ☐ Biological sam	S					
• Will any o		lected in the prevent the medical recorport?	-			
Instrument	A. Patient- reported outcomes (telephone survey)	B. Kidney Supportive Care Implementation Quotient (KSC-IQ) on-line survey with paper option	C. Clinical staff and change team perception of integration of new practices - NOMAD survey on-line survey with paper option	D. Facility level monthly report of utilization statistics	E. Baseline and follow- up patient demographic and utilization data	
Mode of administratio n	Telephone survey	Self- administered on-line survey with paper option	Self- administered on-line survey with paper option	Aggregate data from quality improvement reports	Chart review or EMR report	
Mode of adminis	A. Individual Collecting: gen der, ethnicity, race, age, and education NOTE: Name, phone, email and physical address are obtained only for purposes of contacting patient to enroll them in study and then for mailing incentive gift card and copy of information needed for consent. Name, phone, email, and physical address will not remain linked to survey data.	B. Individual Collecting: employer name	C. Individual No personal or demo data collected	D. Aggregate (by center)	E. Individual Non- identifiable data to be collected Demo include age group, sex, race, Medicaid status (proxy for economic status), ESCO status, primary language, vintage (years in dialysis treatment.	
		ode numbers and direct				
O Yes 🖸 No						
17.3 Protections that	will be implemented to	o maintain the confiden	itiality of data, and s	pecimens:		

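### The KSC-IQ staff survey has no fixed invitation list across its two waves, so partner-organization staff may enter at follow-up only and the before/after change is open to a composition shift of unknown direction

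*Combined protocol and SAP*

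**What the plan says.** KSC-IQ is a summative measure taken twice. On the first wave, section 9.1 B says "The survey will be conducted at baseline prior to inception of the collaborative"; the second follows the close of the collaborative. It bears on the staff-reported part of the hypothesis in 8.2.

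Five places say who is surveyed, and they fall into two groups.

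**Without a change-team condition**
- 9.1 B (survey description): the link goes to local staff of the dialysis center, "associated nephrology offices, and palliative care or hospice organizations cooperating with the dialysis center". Palliative care and hospice organizations need only be cooperating.
- 10.6, criterion 3: "Dialysis personnel working in the participating dialysis centers or associated nephrology practice or associated palliative care practice". Hospice is not named.
- 13.2 (consent table): "All staff of dialysis center, and associated nephrology practices and /or palliative care practices". Hospice is not named here either.

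**With a change-team condition**
- 9.1 B (procedure, step 1): "In the case where the change team has identified such partner organizations, those organizations will send a survey link to all of its staff".
- 10.1 B: after inviting all employees of the center or its associated CKD practices outright, it adds that staff of associated offices are invited in some cases, and then: "This invite will be extended if the change team is implementing change practices in conjunction with the nephrology clinic or palliative care clinic".

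Section 8.3 lists among the immediate impacts of the change package "Nephrology practices and dialysis centers engaging in collaborative efforts with palliative care" and hospice programs. Section 10.1 B says individuals will not be tracked between waves. The data table in section 17 shows that the survey records the employer ("Collecting: employer name"). Section 8.4 describes no analysis that uses it.

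**The concern.** In an uncontrolled before/after comparison with no linkage of individuals, the two waves must sample the same population for the difference in means to be read as change. Under the conditional wording, whether a partner organization is surveyed depends on what the change team is doing with it. The first wave is taken before the collaborative begins, and the collaborative aims to create this kind of joint work. Even the milder condition in the 9.1 B description, that a palliative care or hospice organization be cooperating, is a status the intervention is meant to alter.

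Staff of palliative care and hospice programs may rate supportive-care delivery differently from dialysis staff. If some of them answer only at follow-up, a center's mean KSC-IQ score shifts because different people were asked. This would occur at the centers that added partners, so it could be taken for an implementation effect if partner staff score higher, or hide a real one if they score lower. No comparison group is available to separate the two.

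**Working it through.** **1. The plan's own figures.** Section 10.1 B anticipates up to 750 respondents per wave, with about 40-50 staff per site.
- 15 sites × 50 = 750, which matches; 15 × 40 = 600. So 750 is the upper end.
- 360 patients + 750 + 150 NoMAD respondents = 1,260 per wave, and 2 × 1,260 = 2,520, as in 10.4.
- No separate allowance for partner staff is visible. Equal totals of 750 and 750 do not show equal composition.

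**2. Which staff can enter at follow-up only?**
- Dialysis-center staff: invited in both waves under every section. Not exposed.
- Associated CKD or nephrology practice staff: invited outright in the first sentence of 10.1 B and in the 9.1 B procedure, but conditionally later in 10.1 B. The text conflicts.
- Palliative care and hospice staff: conditional on change-team activity in the 9.1 B procedure, on cooperation in the 9.1 B description and, for palliative care only, on implementation in 10.1 B; unconditional for palliative care in 10.6 and 13.2. The text conflicts, and these are the staff most exposed.

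**3. Size of the shift.** At an affected center,

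shift = (partner share at follow-up − partner share at baseline) × (partner-minus-center score gap, in SD).

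The documents give neither factor. Two assumed cases:
- share up by 20 points, gap 0.5 SD: 0.20 × 0.5 = 0.10 SD
- share up by 30 points, gap 0.8 SD: 0.30 × 0.8 = 0.24 SD

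With a smaller assumed gap of 0.2 SD and a share rise of 10 to 30 points, the shift is only 0.02 to 0.06 SD.

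**4. Effect on the planned test.** Section 8.4 uses a two-sided one-sample t test on matched differences. Assumed: 15 center differences (14 df), 30 respondents per center per wave, SD of true center change 0.2, two-sided alpha 0.05 (8.4 states no alpha).

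SD of a center difference = √(2/30 + 0.2²) = √0.1067 = 0.327

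SE of the mean = 0.327/√15 = 0.084

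If k of 15 centers are affected, the mean shift is (k/15) × shift. The chance of rejecting when average perception has not changed, from the noncentral t for k = 15 and from simulation for k = 5 and 7, is:

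| Centers affected | Shift 0.10 SD: mean shift | Rejection | Shift 0.24 SD: mean shift | Rejection |
|---|---|---|---|---|
| 5 of 15 | 0.033 | 6% | 0.080 | 12% |
| 7 of 15 | 0.047 | 8% | 0.112 | 20% |
| 15 of 15 | 0.100 | 20% | 0.240 | 75% |

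With the same composition in both waves the shift is 0 and the rate is the nominal 5%.

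**The case against.** A reader might infer that partner staff become eligible only once the change team works with them, so that the intervention decides who is surveyed and the staff-reported change is confounded. The documents do not support that.
- The 9.1 B description, 10.6 and 13.2 carry no change-team condition, and the 9.1 B description covers the baseline wave too.
- Section 10.1 B invites associated CKD practices outright.
- A partner can be identified before baseline and so be invited twice.
- Section 8.3 does not say that such collaboration was absent at the start.

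A reader might also take 75% as the size of the problem. That needs the largest assumed share and the largest assumed gap, at all 15 centers. Section 10.1 B expects associated offices to be invited only in some cases, so the rows for 5 or 7 centers are closer to the plan's wording. Nor can the direction be presumed.

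Section 8.4 does plan to match the post sample to the pre sample on cluster size and pre-treatment variables, with regression for residual imbalance. It names no staff variable, so it cannot be counted as closing the gap. Survey timing is also listed in an attached measures spreadsheet that is not part of the text reviewed, and it might say more.

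These objections stand against the stronger claim. They do not remove the narrower one: the sections disagree on who is invited, nothing fixes the list, and under one stated rule some partners would be asked only at follow-up.

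**Conclusion.** The point holds as a risk that the plan leaves open. The KSC-IQ invitation list is defined inconsistently and is not held constant across waves, so the before/after staff comparison is exposed to a composition shift, of unknown direction, at centers that add partners. Dialysis-center staff are outside it.

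Its size cannot be derived from the documents. Under the assumptions shown, false rejection runs from barely above nominal (6%) to about 20% when 5 to 7 centers are affected; higher figures require nearly every center to be affected. The omission of hospice from 10.6 and 13.2 is a wording mismatch to be reconciled, not in itself evidence of bias. The change is worth making because the bias path follows from a stated rule and closing it needs no new data.

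**What to change.** 1. Reconcile both parts of 9.1 B with 10.1 B, 10.6 and 13.2 on which organizations' staff are invited, including hospice staff.
2. Record each site's list of invited organizations at baseline and re-invite that list at follow-up.
3. In 8.4, make the main before/after KSC-IQ comparison among staff of employers invited in both waves, using the employer field already collected.
4. Report staff of partners added later separately, at follow-up only.

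The cost is protocol and analysis wording, plus keeping one list per site. The downside is that responses from later-added partners leave the before/after comparison. The fix holds the invited organizations constant; it does not equalize response rates between center and partner staff, so respondents by employer should be shown for each wave.
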